6.1.2 AE date imputation

6.1.2.1 AE Start Date Imputation

If the adverse event start date was entirely missing or patient has not yet started study treatment no imputation was done.

1. If the AE start date year value is missing, the date uncertainty is too high to impute a rational date. Therefore, if the AE year value is missing, the imputed AE start date is set to NULL.
2. If the AE start date year is available and the year is less than year of the treatment start date, the AE started before treatment. Therefore:
 - a. If the AE year is less than the treatment year and the AE month is missing, the imputed AE start date is set to the mid year point (01JulYYYY).
 - b. Else if the AE year is less than the treatment year and the AE month is not missing, the imputed AE start date is set to the mid month point (15MONYYYY).
3. If the AE start date year is available and value is greater than the treatment start date year value, the AE started after treatment. Therefore:
 - a. If the AE year is greater than the treatment year and the AE month is missing, the imputed AE start date is set to the year start point (01JanYYYY).
 - b. Else if the AE year is greater than the treatment year and the AE month is not missing, the imputed AE start date is set to the month start point (01MONYYYY).
4. If the AE start date year value is equal to the treatment start date year value:
 - a. And the AE month is missing or the AE month is equal to the treatment start month, the imputed AE start date is set to one day after treatment start.
 - b. Else if the AE month is less than the treatment start month, the imputed AE start date is set to the mid month point (15MONYYYY).
 - c. Else if the AE month is greater than the treatment start month, the imputed AE start date is set to the start month point (01MONYYYY).

The table below presents the algorithm used to impute the partial AE start date:

| | MON MISSING | MON < TRT_MON | MON = TRT_MON | MON > TRT_MON |
|------------------------------|------------------------|------------------------------|------------------------------|------------------------------|
| YYYY MISSIN G | _null_ | _null_ | _null | _null_ |
| YYYY < TRT_YR | 01JULYYYY Y | 15MONYYYY | 15MONYYYY | 15MONYYYY |
| YYYY = TRT_YR | TRTSTD+1 | 15MONYYYY | MAX(01MONYYY Y, TRTSTD+1) | MAX(01MONYYY Y, TRTSTD+1) |
| YYYY > TRT_YR | 01JANYYY Y | MAX(01MONYYY Y, TRTSTD+1) | MAX(01MONYYY Y, TRTSTD+1) | MAX(01MONYYY Y, TRTSTD+1) |

Where:

MON = Month of Partial Adverse Event Start Date

AE_YR = Year of Partial Adverse Event Start Date

TRT_MON = Month of Treatment Start Date

TRT_YR = Year of Treatment Start Date

TRTSTD = Treatment Start Date

6.1.2.2 AE End Date Imputation

Rules for imputing the AE end date:

- Rules for imputing the AE end date:
- If AE day is missing but year and month are available, then the AE end date is set to minimum of (end date of follow-up period (treatment end date + 30 days), last day of the month, date of death, cutoff date).
- If AE month and day are missing but year is available, then it is set to minimum of (end date of follow-up period, Dec-31 of the year, date of death, cutoff date).
- If AE year is missing the end date will not be imputed.
- If complete (imputed) AE end date is available and the imputed AE start date is greater than the (imputed) AE end date, then imputed AE start date should be set to the (imputed) AE end date. If patient has not yet started study treatment, no imputation will be done for AE end date.

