2.1.1.8 On-treatment assessment/event

Safety summaries and selected summaries of deaths will summarize only on-treatment assessments/events. On-treatment assessment/event is defined as any assessment/event obtained in the time interval:

Date of first administration of study treatment through the date of last administration of study treatment + 30 days, i.e. including the lower and upper limits.

Adverse events that begin or worsen after informed consent should be recorded in the Adverse Events CRF. Conditions that were already present at the time of informed consent should be recorded in the Medical History page of the patient's CRF.

If the last date of study treatment is missing, on-treatment assessments/events include any assessment/event recorded in the database and which occur after the start date of study treatment.

Data listings will include all assessments/events, flagging those which are not on-treatment assessments/events.

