3.8.1 Adverse events (AEs)

Adverse events will be assessed according to the Common Terminology Criteria for Adverse Events (CTCAE) version 4.03. If CTCAE grading does not exist for an adverse event, the severity of mild, moderate, severe, and life-threatening, corresponding to Grades 1 - 4, will be used. CTCAE Grade 5 (death) will not be used in this study; rather, information about deaths will be collected through the Study Evaluation Completion page. Adverse events will be coded using the most recent version of the medical dictionary for regulatory activities (MedDRA) available at the time of each analysis.

The AEs experienced by the patients in all the observation periods will be listed. The AEs reported in pre-treatment and post-treatment period will be flagged in the listing. In an AE listing, details will be provided for severity grade of AE, seriousness of AE, its relationship to

study treatment, its duration, action taken, outcome, and whether medication or therapy was given to patient.

Treatment Emergent AEs are those, which start in on-treatment period, or which start in pre-treatment period but worsen in on-treatment period. Summary tables for all TEAEs will be provided by study treatment group.

AEs will be summarized by number and percentage of subjects having at least one AE, having at least one AE in each primary system organ class (SOC) and for each preferred term (PT) using MedDRA coding. A subject with multiple occurrences of an AE will be counted only once in the respective AE category. A subject with multiple CTCAE grades for the same preferred term will be summarized under the maximum CTCAE grade recorded for the event. The tables will be summarized alphabetically by SOC and in decreasing frequency of PTs. The decreasing order of PTs will be based on the total count.

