6.1.3.2 Concomitant medication end date imputation

Rules for imputing the CMD end date (including on-going records CM.CMONGO='Y'):

- If CMD end day is missing and CMD month/year are non-missing:
 - a) If day is missing but month/year are not missing impute day with the last day of the month.
- If CMD end day/month are missing and CMD year is non-missing:
 - a) If CMD year is prior to or greater than the year of first dose of treatment, assume the 31 Dec.
 - b) Else if CMD year is equal to the year of first dose of treatment, the imputed end date is the min of (treatment end date, 31st of December).
- If imputed CMD end date is less than the CMD start date, use the CMD end date as the imputed CMD start date.
- If imputed CMD end date is greater than date of death, date of cutoff, or end date of follow-up period, then the imputed CMD end date will take the minimal date among date of death, date of cutoff, or end date of follow-up period.

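### Partial AE end dates are capped at last dose + 30 days even when the recorded month or year is later, so some post-treatment AEs can be counted as treatment-emergent

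*SAP*

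**What the plan says.** **AE end dates (SAP 6.1.2.2).** With the day missing, "the AE end date is set to minimum of (end date of follow-up period (treatment end date + 30 days". The other candidates for the minimum are the end of the recorded month, death and the data cut-off. With day and month missing, the end is the "minimum of (end date of follow-up period, Dec-31 of the year, date of death, cutoff date". If the imputed start is later than the end, "then imputed AE start date should be set to the (imputed) AE end date".

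**AE start dates (SAP 6.1.2.1).** A start with a known month after the treatment-start month, or in a later year, goes to the first of that month. With no year, "if the AE year value is missing, the imputed AE start date is set to NULL".

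**Classification.** SAP 2.1.1.8 runs the on-treatment interval "through the date of last administration of study treatment + 30 days", limits included. SAP 3.8 starts the post-treatment period the day after. SAP 3.8.1 says "Treatment Emergent AEs are those, which start in on-treatment period", or that start before treatment and worsen on it. Pre- and post-treatment AEs are to be flagged in the listing.

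**Medications (SAP 6.1.3.2).** A year-only end date in the first-dose year becomes the earlier of treatment end and 31 December. Next comes: "If imputed CMD end date is less than the CMD start date, use the CMD end date as the imputed CMD start date". A later bullet limits the end date by death, cut-off and end of follow-up.

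**The concern.** An imputation rule should fill in what is unknown without contradicting what is recorded. This one overrides a recorded month or year. End dates beyond last dose + 30 days are to be expected: protocol 8.1.1 follows AEs until they resolve or are judged permanent, and protocol 7.1.6 follows suspected-related AEs until resolution or stabilization.

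The cap is also the last day that counts as on-treatment. Moving a start back to it therefore puts the event on the wrong side of the boundary that SAP 3.8 draws. What is at stake is the treatment-emergent AE tables, the AE durations in the listings, and possibly the flags for prohibited medication during treatment.

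**Working it through.** The documents give no figure to reproduce, so the rules were applied literally to test records. The dates are assumptions for illustration: first dose 1 Mar 2018, last dose 15 Jun 2018, cut-off 30 Jun 2019, no death. The cap and the end of the on-treatment window are then 15 Jun + 30 days = 15 Jul 2018.

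**AEs (SAP 6.1.2.1 and 6.1.2.2)**

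| Case | Recorded start | Recorded end | Start used | End used | Result |
|---|---|---|---|---|---|
| A | Nov 2018 | Dec 2018 | 1 Nov, reset to 15 Jul 2018 | min(15 Jul, 31 Dec) = 15 Jul 2018 | Classed on-treatment; start at least 109 days too early (15 Jul to 1 Nov) |
| B | 5 Nov 2018 | Dec 2018 | 5 Nov 2018 | 15 Jul 2018 | Stays post-treatment; end 113 days before start |
| C | Nov 2018 | 20 Dec 2018, or no end year | 1 Nov 2018 | 20 Dec 2018, or none | Unaffected |
| D | 10 May 2018 | Dec 2018 | 10 May 2018 | 15 Jul 2018 | Correctly on-treatment; end 139 to 169 days too early (15 Jul to 1 or 31 Dec) |
| E | no year | 20 May 2018 | NULL | 20 May 2018 | Neither limb of the treatment-emergent definition can be evaluated |

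Reclassification therefore needs both dates partial and both after the window (case A). A shorter lag gives the same result. With last dose 10 Jan 2019 the cap is 9 Feb 2019, and an AE recorded Mar 2019 to Mar 2019 is placed on 9 Feb, at least 20 days before its recorded month begins.

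**Medications (SAP 6.1.3.2, bullets applied in the order printed)**

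- Complete start 20 Aug 2018, end year 2018: the end becomes min(15 Jun, 31 Dec) = 15 Jun 2018, and the complete start is overwritten with 15 Jun, the last treatment day.
- Same start, end Sep 2018: the end is first 30 Sep, so the start is kept. The follow-up limit then gives 15 Jul, 36 days before the start.
- Start 1 Feb 2019, end year 2019: the start is kept, and the end becomes 15 Jul 2018, again before the start.

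**Effect of one reclassified patient on an incidence**

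- Phase I cohort of 8 (protocol 1.2.5.1.2): 100/8 = 12.5 points.
- Phase II overall, 46 + 33 = 79 recruited (SAP section 4): 100/79 = 1.3 points.
- By group: 100/46 = 2.2 and 100/33 = 3.0 points.

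These are upper bounds. SAP 3.8.1 counts a subject once per category, so incidence moves only if that patient has no other qualifying event there. SAP 3.8 tabulates Phase II safety overall, while 3.8.1 refers to study treatment group, so both bases are shown.

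**The case against.** The strongest reply is that this will hardly ever happen. Routine AE and medication collection runs to about 30 days after last dose (protocol 7.1.6; 8.1.1 extends AE monitoring to 5 half-lives if longer). Later SAEs are reported only if suspected related, within 24 hours of learning of them (protocol 8.2.2), and missing values are queried (protocol 9.4). A late event with both dates partial should be rare. AE duration appears only in listings, and complete dates are mostly untouched. All of this stands, and it is why severity is low. It does not make the rule right.

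Some stronger readings are tempting, but the documents do not support them:

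- **That late AEs in general are pulled into the on-treatment period.** Only those with both dates partial are. The reset names the imputed start only.
- **That any partial medication end date overwrites the start.** In the printed order the replacement step precedes the follow-up limit, so only a year-only end in the first-dose year triggers it.
- **That AEs without a start year are dropped from the treatment-emergent tables.** A literal program would probably omit them, but the SAP states no such exclusion, and all AEs are listed. What is missing is a classification rule.
- **That the per-protocol set changes.** SAP 2.3.1 identifies prohibited drugs as deviations in the database and does not say that imputed dates decide this. SAP 2.2.5 excludes only major violations, and its clinical benefit analysis is optional. Concomitant-medication counts do not change either, because SAP 3.1.6 includes any start on or after first dose.

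**Conclusion.** Wrong as written, low severity. For AEs, the cap can contradict a recorded later month or year in three ways. It reclassifies a post-treatment AE as treatment-emergent when both dates are partial. It puts the end before a complete start. It lists an on-treatment AE as ending before its recorded month of resolution. For medications, a drug begun after treatment can be dated to the last treatment day in one configuration, and in others the end can precede the start. This could affect prohibited-medication flags, but not the concomitant-medication summaries.

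The incidence effect per reclassified patient is at most the figures shown above. The number of partial dates cannot be derived from the documents. The conclusion assumes that the rules are programmed literally and that the medication bullets are applied in the order printed.

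**What to change.** 1. In SAP 6.1.2.2 and 6.1.3.2, impute a partial end date to the last day of the recorded month or year, limited by death and cut-off. Apply the follow-up or treatment-end cap only if the cap date lies within that recorded month or year and is on or after the (imputed) start date.
2. Never move a start before the first day of its recorded month or year, never overwrite a complete start, and never let an imputed end precede the start.
3. As a secondary clarification in 6.1.2.1 and 3.8.1, state how AEs with a NULL start are classified, for example as treatment-emergent unless the end date is before first dose. SAP 6.1.3.1 already supplies a start date for medications with no start year.

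Under this rule case A keeps 1 Nov to 31 Dec 2018 and is post-treatment. The condition on the start date in step 1 is needed. A cap kept whenever the recorded year is not later than the cap would still fail for a year-only end. With last dose 10 Jan 2019, a complete start of 5 Mar 2019 and end year 2019, it would give 9 Feb. The medication started 20 Aug 2018 with end year 2018 would still end on 15 Jun.

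The cost is a few lines of SAP text and date-derivation code. A few more undated AEs may be counted as treatment-emergent, and where the cap no longer applies, a year-only end may run as late as 31 December, death or cut-off.

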6.1.3 Concomitant medication date imputation

6.1.3.1 Concomitant medication start date imputation

Rules for imputing the CMD start date:

1. If the CMD start date year value is missing, the imputed CMD start date is set to one day prior to the date of first dose.
2. If the CMD start date year value is less than the treatment start date year value, the CMD started before the treatment. Therefore:
 - a) If the CMD month is missing, the imputed CMD start date is set to the mid-year point (01JulYYYY).
 - b) Else if the CMD month is not missing, the imputed CMD start date is set to the mid-month point (15MONYYYY).
3. If the CMD start date year value is greater than the treatment start date year value, the CMD started after the treatment. Therefore:
 - a) If the CMD month is missing, the imputed CMD start date is set to the year start point (01JanYYYY).

Else if the CMD month is not missing, the imputed CMD start date is set to the month start point (01MONYYYY).

1. If the CMD start date year value is equal to the treatment start date year value:
 - a) And the CMD month is missing or the CMD month is equal to treatment start month, then the imputed CMD start date is set to one day after the treatment start date.
 - b) Else if the CMD month is less than the treatment start month, the imputed CMD start date is set to the mid-month point (15MONYYYY).
 - c) Else if the CMD month is greater than the treatment start month, the imputed CMD start date is set to the start month point (01MONYYYY).

6.1.3.2 Concomitant medication end date imputation

Rules for imputing the CMD end date (including on-going records CM.CMONGO='Y'):

- If CMD end day is missing and CMD month/year are non-missing:
 - a) If day is missing but month/year are not missing impute day with the last day of the month.
- If CMD end day/month are missing and CMD year is non-missing:
 - a) If CMD year is prior to or greater than the year of first dose of treatment, assume the 31 Dec.
 - b) Else if CMD year is equal to the year of first dose of treatment, the imputed end date is the min of (treatment end date, 31st of December).
- If imputed CMD end date is less than the CMD start date, use the CMD end date as the imputed CMD start date.
- If imputed CMD end date is greater than date of death, date of cutoff, or end date of follow-up period, then the imputed CMD end date will take the minimal date among date of death, date of cutoff, or end date of follow-up period.

6.1.3.3 Prior therapies date imputation

Not Applicable

6.1.3.4 Post therapies date imputation

Not Applicable

6.1.3.5 Other imputations

Not Applicable

6.2 AEs coding/grading

Adverse events will be coded using the Medical Dictionary For Regulatory Activities (MedDRA) version 19.1 or higher.

AEs will be assessed according to the Common Terminology Criteria for Adverse Events (CTCAE) version 4.03 (specify CTCAE version used in the SAP).

6.3 Laboratory parameters derivations

6.3.1 Differential Counts:

CTCAE grading is based on absolute values. However, for some labs this data may not present itself as absolute counts and be recorded as percentage or fraction in the database (e.g. neutrophils).

The following rules will be applied to derive the WBC differential counts when only percentages are available for a xxx differential

xxx count = (WBC count) * (xxx %value / 100)

6.4 Statistical models

6.4.1 Analysis of Response Rate

Patients with clinical benefit, disease control and responders are summarized in terms of percentage rate with 95% confidence interval. An exact binomial confidence interval (implemented using the SAS procedure FREQ with the EXACT statement for one-way tables) is calculated ([Clopper & Pearson, 1934](#)).

The SAS procedure FREQ was used with the following code:

PROC FREQ DATA=*dataset*;

BY *treatment*;

TABLES *response* / binomial;

EXACT binomial;
RUN;

6.4.2 Time to event analysis

The following variables will be used:

- Progression, Survival, Definitive deterioration: Event
- Censoring indicator variable: 1=Censored; 0=Event

